9.8. Echocardiograms/Multigated Acquisition Scans

Left ventricle ejection fraction (LVEF) will be summarized at baseline and post-baseline time points utilizing descriptive statistics, including observed percent LVEF as a continuous variable and numeric change from baseline, number and percentage of patients with grade 3 decreased ejection fraction defined as an observed left ventricular ejection fraction (%) in 20% - 39% or a

CONFIDENTIAL Page 27 of 29

percent reduction of 20% or more from baseline in left ventricular ejection fraction (%) among those patients who have baseline assessment and at least one post-baseline assessment.

9.9. Dermatologic Assessments

The number of patients with new suspicious skin lesions will be summarized overall and by location by number and percent of patients with assessment.

9.10. Prior and Concomitant Medications and Procedures

Prior medications and procedures taken or performed within 30 days prior to screening and prior to the first dose will be documented.

All concomitant medications and procedures (those taken or performed on or after the day of the first dose to 30 days after the last dose of study drug, including those started prior to first dose of study treatment and continued during on-treatment period) will be documented.

Prior and concomitant medications will be summarized by the WHO Drug Dictionary Anatomical Therapeutic Chemical 2nd level (ATC-2) and preferred name for the Safety Population and Ex11 Safety Population. If the ATC-2 level term is not available, the next available level (e.g., ATC-1) will be used.

The number and proportion of the patients who took each medication will be tabulated by the ATC-2 level and preferred name for concomitant medications. A patient will only be counted once within each ATC-2 code and within each preferred name.

All prior and concomitant medication data will be listed by patient.

10. ANALYSIS OF DISRUPTIONS DUE TO COVID-19 PANDEMIC

10.1. Changes in Data Collection due to COVID-19 Pandemic

Under the guidance of the FDA, a COVID-19 Pandemic Impact Form was created to capture the supplemental information regarding the impact of the COVID-19 pandemic on study conduct, including missed visit, out of window visit, televisit/remote visit, local tests, and the other scenarios.

10.2. Analysis of Data Captured due to COVID-19 Pandemic

Study assessments disrupted by COVID-19 pandemic will be listed by site, treatment arm, patient, and scheduled visit. The number of disrupted visits will be tabulated by site and treatment arm.

10.2.1. COVID-19 Adverse Events or COVID-19 Related Deaths

COVID-19 adverse events and COVID-19 related deaths will be presented under COVID-19 terms in the listings.

Analysis of concomitant medications/procedures specifically for COVID-19 related indications may be listed if needed.

CONFIDENTIAL Page 28 of 29

10.2.2. Other Safety Data Captured due to COVID-19 Disruption

Data collected through a televisit will be analyzed together with those collected at on-site visits unless otherwise specified.

Local test data of vital signs, dermatologic exam, 12-Lead ECG, and Echocardigram/MUGA will be analyzed together with those collected at on-site visits unless otherwise specified.

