### 6.11.4. Electrocardiograms

Digital, 12-lead ECGs will be performed with central over-reading according to the schedule of assessments in Table 1 (schedule of assessments). All sites will be provided with an ECG machine and associated materials by the central ECG diagnostic service.

Performance of all ECGs must adhere to the following guidelines:

- All standard digital ECGs must be performed after the patient has been in the supine or semi-recumbent position for at least 15 minutes. The 15-minute rest period will start after the placement of the ECG leads.
- The ECG must be performed before the dose of study drug.

A hard copy of the ECG must be printed and signed by the Investigator at the site.

ECG data will be transmitted to the central ECG diagnostic service and all interval measurements will be reviewed and adjusted using the central ECG core labs methodology by a trained ECG analyst. A cardiologist at the central ECG diagnostic service will then review each ECG to confirm if intervals were calculated correctly and to provide an interpretation. A report containing this information will be provided to the site for review and signature by the Investigator. This report will be filed with the machine ECG report for each visit in the patient's source documents. The values reported by the central ECG diagnostic service will be used for data analysis.

Heart rate and the following ECG intervals will be captured in the database:

- PR interval
- QT, QT interval corrected using Bazett's formula (QTcB) ( $QTcB = QT/RR^{0.50}$ ) and QT interval corrected by Fridericia's formula (QTcF) ( $QTcF = QT/RR^{1/3}$ ) intervals
- QRS duration
- RR interval

The central ECG diagnostic service's standard reference ranges will be used throughout the study.

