### 6.11.5. Echocardiograms/Multigated Acquisition Scans

Echocardiograms or multigated acquisition scans (MUGAs) will be performed according to [Table 1](#) (schedule of assessments). Echocardiogram or MUGA performed as standard of care prior to informed consent may be used as the screening assessment as long as the echocardiogram or MUGA was performed within 28 days prior to the first dose of study drug. The same modality (echocardiogram or MUGA) must be used throughout the study. LVEF must be documented in the patient's source documents and eCRF.

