9.7. Electrocardiograms

PR, QRS, QT, QTc (ie, QTcB and QTcF) and RR intervals and their change from baseline will be summarized for each treatment arm by scheduled visit. Patients will be categorized into >450, >480, or >500 ms per their maximum post-baseline absolute QTc interval and >30, or >60 ms per their maximum change from baseline QTc interval. Additionally, patients will be classified into the following categories: HR \le 50 bpm and/or decrease from baseline \ge 20 bpm; HR \ge 120 bpm and/or increase from baseline \ge 20 bpm; PR \ge 220 ms and/or increase from baseline \ge 20 ms; QRS \ge 120 ms. The number and percentage of patients in each category will be summarized for each treatment group.

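### SAP 10.2.2 pools pandemic-era local ECGs with on-site ECGs without requiring a central read, although protocol 6.11.4 bases ECG analysis on the central service's values

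*SAP*

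**What the plan says.** **Protocol 6.11.4 (Electrocardiograms).** The protocol sets up one measurement process. "Digital, 12-lead ECGs will be performed with central over-reading", and "All sites will be provided with an ECG machine and associated materials by the central ECG diagnostic service". An analyst at the central service reviews and adjusts the intervals, a cardiologist confirms them, and "The values reported by the central ECG diagnostic service will be used for data analysis".

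**SAP 10.2.2 (other safety data under COVID-19 disruption).** "Local test data of vital signs, dermatologic exam, 12-Lead ECG, and Echocardigram/MUGA will be analyzed together with those collected at on-site visits". The sentence closes with an exception for anything specified differently. It says nothing about central reading, a source flag or a sensitivity analysis.

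**SAP 9.7 (Electrocardiograms).** "Patients will be categorized into >450, >480, or >500 ms per their maximum post-baseline absolute QTc interval". Patients are also classed as >30 or >60 ms on their maximum change from baseline. The section does not say which ECG source qualifies.

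**LVEF.** Protocol 6.11.5 keeps one method per patient: "The same modality (echocardiogram or MUGA) must be used throughout the study". Values are recorded at the site in source documents and the eCRF. No central LVEF read is set up.

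**Version.** SAP section 1 states that the SAP is based on protocol Amendment 6, dated 23 October 2020, and that it may modify the protocol's plans and supersedes its statistical sections.

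**The concern.** The protocol makes QTc comparable within a patient by having every interval re-measured in one place. SAP 10.2.2 names the 12-lead ECG among the local tests to be pooled and does not carry that condition over. A programmer following it would put a local, unadjusted QTc in the same column as centrally adjusted values.

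For a mean by visit, a few such values would matter little. The tables in SAP 9.7 rest on a maximum, so a single aberrant reading is enough to move a patient into a higher category, and a later normal reading does not move the patient back. Extra measurement noise therefore tends to raise outlier counts in whichever arm it occurs. Comparing the safety profiles of the two drugs is a stated objective, and these categories are part of the cardiac description.

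**Working it through.** **Step 1. The texts side by side.** The plan states no figure on this point, so there is none to reproduce.

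| Question | Protocol 6.11.4 | SAP 9.7 and 10.2.2 |
|---|---|---|
| Whose ECG values are analysed? | The central service's | Local pooled with on-site; source not restricted |
| Is a central read required? | Yes | Not stated for local ECGs |
| How is a patient classified? | Not covered | Maximum QTc and maximum change |

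The exception at the end of the SAP sentence does not resolve this within the SAP, because neither section specifies anything else for ECGs.

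**Step 2. One ECG, no true change.** All SDs here are my assumptions, as the documents give none. Let w be the within-patient SD of a centrally read QTc, and a the extra SD of a local reading that was not centrally read. With a central baseline,

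SD of change = √(2w² + a²), and P(change >30 ms) = 1 − Φ(30 / SD).

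| w (ms) | a (ms) | SD of change (ms) | P(>30 ms) | P(>60 ms) |
|---|---|---|---|---|
| 8 | 0 | 11.3 | 0.4% | <0.001% |
| 8 | 10 | 15.1 | 2.3% | 0.004% |
| 8 | 15 | 18.8 | 5.5% | 0.07% |
| 10 | 0 | 14.1 | 1.7% | 0.001% |
| 10 | 10 | 17.3 | 4.2% | 0.03% |
| 10 | 15 | 20.6 | 7.3% | 0.18% |

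The a = 0 rows are also the answer if local readings are as good as central ones.

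**Step 3. Maximum over several visits.** Treat the m post-baseline changes as independent, a simplification since they share a baseline. Let p0 be the false-positive chance of a central value and p1 that of a local one.

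All central: 1 − (1 − p0)^m. One local: 1 − (1 − p0)^(m−1) × (1 − p1).

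I took m = 4 or 8, a central change SD of 12 or 15 ms, a local change SD of 20 or 25 ms, and a local offset of 0 or 10 ms.

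- Low end (m = 4, central SD 12, local SD 20, no offset): p0 = 1 − Φ(30/12) = 0.62% and p1 = 1 − Φ(30/20) = 6.7%. All central gives 2.5%; one local gives 8.4%.
- High end (m = 8, central SD 15, local SD 25, offset 10): p0 = 1 − Φ(30/15) = 2.3% and p1 = 1 − Φ(20/25) = 21.2%. All central gives 16.8%; one local gives 32.9%.

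For >60 ms, the same grid gives at most 0.03% all central and 0.14-2.3% with one local value. With equal SD and no offset, the two columns are identical.

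**Step 4. What cannot be calculated.** The documents do not say how many ECGs were local, how many of those were centrally read, or how they split by arm. No total for either table can be derived.

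**The case against.** **Local may mean only where the test was done.** SAP 10.2.2 does not say that local ECGs bypass the central service, and nothing in it revokes the protocol's central reading. The closing exception could be read as preserving the protocol rule. This stands in part: a reader might infer that the SAP puts unread machine values into the tables, and the documents do not go that far. They leave it open. The SAP neither cites the protocol rule nor repeats it where the tables are defined, so the default is pooling.

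**The SAP may modify the plan.** Its precedence clause names the statistical sections of the protocol, and the ECG rule is in an assessment section. If a change was intended, it is not declared.

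**The comparison may cross versions.** This stands. The supplied protocol plans no interim analyses, while the SAP has two for OS, and the laboratory tables differ on amylase. The supplied text may predate Amendment 6, so its ECG wording has to be checked.

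**Much is already traceable.** SAP 10.1 has a COVID-19 impact form that captures local tests, and SAP 10.2 lists disrupted assessments by patient and visit. This makes a fix feasible, but the SAP does not provide for a centrally-read flag.

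**Leaving readings out could hide a real prolongation.** If the local ECG is the only one at a visit, including it is the cautious choice. This stands as an argument against simple exclusion, which is why the fix keeps a repeat table.

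**Does it extend to LVEF?** A reader might infer that local echocardiogram or MUGA results are unread values mixed with central ones. The documents do not support that: the protocol has no central LVEF read, and SAP 10.2.2 does not permit a change of modality, so the rule in protocol 6.11.5 still stands. The SAP merely omits to say what happens if a local test used the other modality. That is a gap for clarification and not a conflict.

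**Conclusion.** The point holds for ECGs, at minor severity. On the texts supplied, SAP 10.2.2 pools local ECGs with no central-read condition, protocol 6.11.4 bases analysis on central values, and SAP 9.7's use of maxima lets one uncorrected value set a patient's category.

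Under the Step 2 assumptions, the false >30 ms rate per ECG goes from 0.4-1.7% to 2.3-7.3%. The >60 ms rate stays below 0.2%, though Step 3's wider assumptions take it to 2.3% per patient. I have not quantified the absolute >450, >480 and >500 ms categories. All of this rests on assumed SDs and on at least some local ECGs having no central read. The effect is nil if local readings are no noisier and have no offset.

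A reader might infer that the drug comparison is distorted in favour of one arm, or that efficacy results are touched. Neither follows. The documents give no split of local ECGs by arm, these tables are descriptive counts and percentages, and no efficacy test or alpha is involved.

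**What to change.** 1. Check the ECG section of protocol Amendment 6. If it already provides for local ECGs, align SAP 9.7 and 10.2.2 with it.
2. Otherwise, state in both SAP sections that the QTc change-from-baseline and outlier tables use centrally read values, including local ECGs that were sent for central reading.
3. Flag and list local ECGs that were not centrally read.
4. Repeat the outlier tables with those readings included, so that no possible prolongation is lost and the reader can see whether they matter.
5. As a minor clarification, add to SAP 9.8 that LVEF change is computed within the baseline modality, with any other result flagged.

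The cost is a few sentences, a source flag that the COVID-19 form should help to populate, and one repeat of the ECG outlier tables. The downside is that a few pandemic-era readings appear only in the listing and the repeat table.
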